9.2 Subject Accountability

The disposition of all enrolled subjects will be tabulated by treatment dose group **received on study day 1.** The summary will include the number of subjects who are enrolled, the number and percent of subjects who received/never received the IP, who completed IP, discontinued IP and reasons for discontinuing, who completed the **study**, and who withdrew prematurely from the study before completion of the 24-week treatment period and their reasons for withdrawal.

Key study dates for the first subject enrolled, last subject enrolled, last subject's end of investigational product, last subject's end of study will be presented.

The number and percent of subjects enrolled will be tabulated by study site.

9.3 Important Protocol Deviations

Important Protocol Deviations (IPDs) categories are defined by the study team before the first subject's initial visit and updated during the IPD reviews throughout the study prior to database lock. These definitions of IPD categories, subcategory codes, and descriptions will be used during the course of the study. Eligibility deviations are defined in the protocol.

9.4 Demographic and Baseline Characteristics

Subject demographic and baseline characteristics will be summarized using descriptive statistics by country and overall study population using FAS. If multiple races have been reported for a subject, the subject will be categorized as multiple races.

The following demographic and baseline characteristics will be summarized:

- Age
- Sex
- Ethnicity
- Race
- Targeted neurological disease diagnosis at baseline
- Disease duration of migraine
- Age at onset of migraine
- Monthly migraine days during baseline period
- Acute headache medication days (AHMD) during baseline
- **Acute headache medication used during baseline**
- MFIQ domain scores of function (physical, usual activities, social, and emotional) and overall impact on usual activities global item score at baseline
- **Female subjects of child bearing potential and those with menstrual related migraine (yes/no)**
- Plasma CGRP levels during baseline
- Migraine **classification at screening** (EM/CM)
- Aura (yes/no) **during baseline**
- Prior migraine **preventive** treatment use
- **Triptan medication used during baseline**
- **Triptan medication days during baseline**

9.5 Efficacy Analyses

Detailed analysis methods and covariates included in the models are summarized in the table below.

Table 6. Analysis of Primary Efficacy Endpoint to be Performed by deCODE

Endpoint	Primary Summary and Analysis Method
Achievement of at least a 50% reduction from baseline in mean monthly migraine days (MMD) over months 4, 5, and 6 in relation to each individual genome-wide significant single-nucleotide polymorphism (SNP) contributing to	This analysis is planned to be performed by deCODE and details of the analysis are described in deCODE Analysis Plan (Appendix B).

Endpoint	Primary Summary and Analysis Method
the migraine polygenic risk score (mPRS)	

Table 7. Analysis of Exploratory Efficacy Endpoint to be Performed by deCODE

Endpoint	Primary Summary and Analysis Method
Change from baseline in monthly AMSMD over months 4, 5, and 6, in relation to mPRS	This analysis is planned to be performed by deCODE and details of the analysis are described in deCODE Analysis Plan (Appendix B).
mPRS in relation to baseline CGRP level	
mPRS in relation to baseline MMD	
mPRS in relation to baseline AMSMD	
mPRS in relation to baseline acute headache medication days (AHMD)	
mPRS in relation to Migraine Functional Impact Questionnaire (MFIQ) individual domain scores (physical function, usual activities, social function, and emotional function) and overall impact usual activities global item score at baseline	
mPRS in relation to presence of aura during baseline	
mPRS in relation to baseline mean migraine severity	
Change from baseline in MFIQ individual domain scores (physical function, usual activities, social function and emotional function) and overall impact usual activities global item score at month 6, in relation to mPRS	
Published migraine SNPs in relation to baseline CGRP	

Table 8. Analysis of Exploratory Efficacy Endpoints to be Performed by Amgen

Endpoint	Primary Summary and Analysis Method
Change from baseline in MMD over months 4, 5, and 6 in relation to baseline CGRP level	
 1. Summary statistics by visit using observed data at each visit, and the calculated mean monthly migraine days over month 4, 5 and 6. 2. Estimated slope for baseline CGRP, associated 95% CI and nominal p-value from a linear

Endpoint	Primary Summary and Analysis Method
	
regression model including baseline CGRP, age, sex, dose switch (yes/no), baseline dose (full sample analysis only), and baseline MMD value as covariate using observed data. Dose switch was excluded for 140 mg treatment group.
 
3. Spearman correlation between baseline non-transformed CGRP and Change from baseline in MMD over months 4, 5, and 6.
 
4. A scatterplot with loess will developed for CGRP level with change from baseline in monthly MMD over months 4, 5, and 6.

Achievement of at least a 50% reduction from baseline in mean MMD over months 4, 5, and 6 in relation to baseline CGRP level	
1. Summary statistics based on observed data.2. Odds ratio estimate for baseline CGRP, associated 95% CI, and nominal p-value from a logistic regression model with baseline CGRP level as covariate along with baseline MMD, dose switch (yes/no), baseline dose (full sample analysis only), age and sex. Dose switch was excluded for 140 mg treatment group.3. Predicted probabilities of achieving at least a 50% reduction in MMD
Achievement of at least a 75% reduction from baseline in mean MMD over months 4, 5, and 6, in relation to baseline CGRP level	Same as above.
Change from baseline in monthly AMSMD over months 4, 5, and 6, in relation to baseline CGRP level	
1. Estimated slope for baseline CGRP, associated 95% CI and nominal p-value from a linear regression model including baseline CGRP, age, sex, dose switch (yes/no), baseline dose (full sample analysis only), and baseline AMSMD value as covariate using observed data. Dose switch was excluded for 140 mg treatment group.2. Spearman correlation analysis will be applied between baseline CGRP and change from baseline in monthly AMSMD over months 4, 5, and 6.3. A scatterplot with loess will developed for CGRP level with change from baseline in monthly AMSMD over months 4, 5, and 6.
Baseline MMD in relation to baseline CGRP level	
1. Summary statistics using observed data.2. Estimated slope for CGRP, associated 95% CI and nominal p-value from a linear regression model including age, sex, country (full sample analysis only), and baseline CGRP as covariate using observed data.3. Spearman correlation between baseline CGRP and baseline MMD.

Endpoint	Primary Summary and Analysis Method
Baseline AMSMD in relation to baseline CGRP level	
1. Summary statistics using observed data.2. Estimated slope for CGRP, associated 95% CI and nominal p-value from a linear regression model including age, sex, country (full sample analysis only), and baseline CGRP value as covariate using observed data.3. Spearman correlation between baseline CGRP and baseline AMSMD.
Baseline AHMD in relation to baseline CGRP level	
1. Summary statistics using observed data.2. Estimated slope for CGRP, associated 95% CI and nominal p-value from a linear regression model including age, sex, country (full sample analysis only), and baseline CGRP value as covariate using observed data.3. Spearman correlation between baseline CGRP and baseline AHMD.
Baseline mean migraine severity in relation to baseline CGRP level	
1. Summary statistics using observed data.2. Estimated slope for baseline CGRP, associated 95% CI and nominal p-value from a linear regression model including age, sex, country (full sample analysis only), and baseline CGRP as covariate using observed data.3. Spearman correlation between baseline CGRP and baseline mean migraine severity.
Presence of aura during baseline in relation to baseline CGRP level	
1. Summary statistics using observed data.Estimated odds ratio for baseline CGRP, associated 95% CI and nominal p-value from a logistic regression model including age, sex, country (full sample analysis only), and baseline CGRP using observed data.
Each MFIQ individual domain score (physical function, usual activities, social function, and emotional function) and overall impact usual activities global item score at baseline in relation to baseline CGRP level	
1. Summary statistics using observed data.2. Estimated slope for baseline CGRP, associated 95% CI and nominal p-value from a linear regression model including age, sex, country (full sample analysis only), and baseline CGRP as covariate using observed data.3. Spearman correlation between baseline CGRP and baseline MFIQ score.
Change from baseline in MFIQ individual domain scores (physical function, usual activities, social function, and emotional function) and overall impact usual activities global item score at month 6	
1. Summary statistics using observed data.2. Estimated least squares means and associated 95% CI from an ANCOVA model including age, sex, dose switch (yes/no), baseline dose, and baseline MFIQ score as covariate using observed data.

Endpoint	Primary Summary and Analysis Method
Change from baseline in mean MMD over months 4, 5, and 6	1. Summary statistics using observed data. 2. Least squares means and associated 95% CI from a generalized linear mixed effect model including visit , age, sex, dose switch (yes/no) , baseline dose (full sample analysis only) , and baseline value as covariate using observed data for all assessment timepoints. Dose switch was excluded for 140 mg treatment group. A LSM will be presented for change from baseline at each assessment timepoints, and a LSM comparing change from baseline over months 4, 5, 6 will be presented using contrasts.
Change from baseline in MMD at assessment timepoints	
Change from baseline in mean monthly AMSMD over months 4, 5, and 6	
Change from baseline in monthly AMSMD at assessment timepoints	
Change from baseline in mean monthly AMHD over months 4, 5, and 6	
Change from baseline in monthly AHMD at assessment timepoints	
Achievement of at least a 50% reduction from baseline in mean MMD over months 4, 5, and 6	1. Summary statistics based on observed data.
Achievement of at least a 50% reduction from baseline in MMD at assessment timepoints	
Achievement of at least a 75% reduction from baseline in mean MMD over months 4, 5, and 6	
Achievement of at least a 75% reduction from baseline in mean MMD at assessment timepoints	

9.5.1 Analyses of Primary Efficacy Endpoint(s)

Analyses for the primary endpoint will identify the migraine SNPs significantly associated with clinical response of achievement of at least a 50% reduction from baseline in mean MMD over months 4, 5, and 6 and will be performed by deCODE. Details of this analysis are outlined in deCODE Analysis Plan (Appendix B).

9.5.2 Analyses of Exploratory Efficacy Endpoint(s)

The exploratory endpoints except the endpoints related to genetic biomarkers will utilize the EAS. **All models described below will include covariates as specified in Section 4.1.**

The continuous exploratory efficacy endpoints at each assessment time point or as the mean over months 4, 5, and 6 of the 6-month OLTP will be analyzed using the generalized linear mixed effects model that includes **visit and** baseline values of the endpoint, without any imputation for missing data. Least squares means and associated 95% CI will be reported.

The continuous exploratory efficacy endpoints involving two cross-sectional measures (eg. Change from baseline in MMD at week 12 [endpoint], in relation to change from baseline in CGRP level at week 12 [factor]) will be analyzed using a linear regression model that includes corresponding baseline values and the **variable** of interest as covariates without any imputation for missing data. Estimated slope for the **variable of interest**, associated 95% CI, and nominal p-value from the same model will be reported.

The continuous exploratory efficacy endpoints with relation to a factor (eg. baseline CGRP) will be analyzed using the generalized linear **regression** model that includes corresponding baseline values and the factor as covariate without any imputation for missing data. Estimated slope for the factor, associated 95% CI and nominal p-value from the same will be reported. Least square means and 95% CI corresponding to selected baseline values of the factor (eg. quintiles) will be reported.

The continuous exploratory efficacy endpoints involving change from baseline MFIQ at week 24 will be analyzed using an ANCOVA model including baseline score as covariates without any imputation for missing data. Least squares means and associated 95% CI will be reported.

The dichotomous efficacy endpoints with relation to a factor (eg. baseline CGRP) will be analyzed using logistic regression model **including the factor of interest as a covariate and** without any imputation of missing data. Odds ratios with associated 95% confidence intervals and p-values will be reported. Otherwise, descriptive statistics using **observed data** will be summarized.

The analysis of exploratory endpoints with mPRS will be performed by deCODE and details of the analysis are **outlined** in deCODE Analysis Plan ([Appendix B](#)).

9.6 Safety Analyses

9.6.1 Adverse Events

The Medical Dictionary for Regulatory Activities (MedDRA) version 22.0 or later will be used to code all events categorized as adverse events to a system organ class and a

preferred term. All AEs will be graded using the Common Terminology Criteria for Adverse Events (CTCAE) Version 4.03.

The subject incidence of adverse events will be **presented for the following groups:** (1) subjects always receiving 70mg, (2) subjects who switched from 70mg to 140mg at any time during the study, (3) subjects who switched from 140mg to 70mg at any time during the study, (4) subjects always receiving 140mg, (5) overall – all subjects combined. The subject incidence rates will summarized by **SOC in alphabetical order and PT in descending order of frequency** for all treatment-emergent adverse events, serious treatment-emergent adverse events, treatment-emergent adverse events leading to withdrawal of investigational product, treatment-emergent adverse device effect, **treatment-related adverse events, treatment-related serious adverse events**, and fatal adverse events, **and adverse events of interest (EOI) including:**

- Ischaemic Central Nervous System Vascular Conditions SMQ (Narrow)
- Ischaemic Heart Disease SMQ (Narrow and Broad)
- Peripheral Arterial Disease AMQ (Narrow)
- Hypertension SMQ (Narrow and Broad)
- Constipation AMQ (Narrow and Broad)
- Alopecias AMQ (Broad)
- COVID-19 SMQ (Narrow)

Summaries of treatment-emergent adverse events and serious treatment-emergent adverse events will be tabulated by system organ class, preferred term, and CTCAE grade.

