5.1.3 Safety Endpoints

Treatment-emergent Adverse Event (TEAE)

An event categorized as “Adverse Event” on the Events eCRF starting on or after first dose of investigational product, as determined by “Did event start before first dose of investigational product” equal to “No” or missing, and up to the End of Study date.

Serious Treatment-emergent Adverse Event

A treatment-emergent adverse event with the indicator flag “Serious” equal to “Yes” on the Events eCRF.

Treatment-emergent Adverse Device Effect

A treatment-emergent adverse event with the indicator flag “Is there a reasonable possibility that the event may have been caused by the investigational device” equal to “Yes” on the Events eCRF.

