5.4.3 Study Period

Baseline period is defined in **Table 3** and **Table 4** respectively. The efficacy and safety analyses will be summarized for the OLTP. The analysis window will be defined with the starting time point given by study day 1 after the 1st IP dose and end time point given by EOS date.

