5.5 Subject Disposition

Exposed to Investigational Product

Subjects are defined as exposed if they receive at least one dose of investigational product. Subjects will be defined as having received IP if the observed data indicates they have received IP (IP date is non-missing) on a specific date, even if the IP quantity field is missing (IPQTY = NULL).

Completing the Investigational Product

Subjects are defined as completing investigational product if they complete IP at week 20. It will be derived from the End of IP eCRF with “Completed” as the primary reason for ending IP.

Completing Study

Subjects are defined as completing study if they complete the entire 24 weeks of study evaluation. It will be derived from the End of Study eCRF with “Completed” as the primary reason for ending study.

On-study

Subjects are considered on-study if they are enrolled and have not yet completed their EOS visit.

Dose Switch

Per protocol, dose switch is permitted at the discretion of the investigator at week 12. However, subjects could switch dose before or after week 12 if needed (e.g., adverse event). We define dose switch as an indicator variable indicating is a subject's dosage changed from their baseline dose at any time during the study.

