5.6 Arithmetic Calculations

Migraine Disease Duration

The number of years from the diagnosis date (DXDT) of migraine (migraine with aura or migraine without aura, whichever is earlier) to the date informed consent is signed.

Observed Portion	Missing Portion	Duration of Migraine (Years)
Year, Month, Day	NA	(Informed Consent Date – DXDT) / 365.25
Year, Month	Day	[Year(Informed Consent Date) – Year(DXDT)] + [Month(Informed Consent Date) – Month(DXDT)] / 12 ^a
Year	Month, Day	[Year(Informed Consent Date) – Year(DXDT)] ^a

^a If it equals 0, add 1/12 years (ie, 1 month) to avoid a disease duration of 0.

Age at Onset of Migraine

Age at onset of migraine is defined as Age – duration of migraine.

Duration of IP Exposure

If subject switches dose,

- Duration before the First Switch = Minimum (Last Initial Dose Date + 27, First Switch Dose Date – 1) – First Dose Date + 1
- Duration on or after the First Switch = Minimum (Last Dose Date + 27, EOS Date) – First Switch Dose Date + 1

Otherwise,

- Duration = Minimum (Last Dose Date + 27, EOS Date) – First Dose Date + 1

Change From Baseline

Post-baseline monthly value – Baseline, as defined in Section [5.4](#).

If the baseline or post-baseline value is missing, the change from baseline value will be set to missing.

Percent Change From Baseline

The change from baseline divided by baseline and multiplied by 100:

$$(\text{Post-baseline} - \text{Baseline}) * 100 / \text{Baseline}$$

If the baseline value is 0 and the post-baseline value is also 0, the percent change from baseline is set to 0. If the baseline value is 0 and the post-baseline value is non-zero, then the percent change from baseline is set to missing.

Mean Monthly Change From Baseline Over Multiple Months

Arithmetic Mean monthly change from baseline is the arithmetic mean of the observed monthly change from baseline values for the months with non-missing change from baseline values.

Subject Incidence

The subject incidence for a given event in a given period is defined as the number of subjects with at least one reported occurrence of the event divided by the number of subjects who enter that period (ie, number of at-risk subjects). For subjects with multiple occurrences of the same event, the event will only be counted once per subject.

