9.6.2 Exposure to Investigational Product

The total length of investigational product exposure **and exposure by dose level**, the total dose of investigational product, and the proportion of subjects receiving each dose will be summarized using descriptive statistics.

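### Adverse event incidence is tabulated only by whole-study dose-switch history plus overall, so the switch columns mix events on two doses and no table gives events by dose at onset

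*SAP*

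**What the plan says.** SAP 9.6.1 sets out five groups for subject incidence of adverse events: "1) subjects always receiving 70mg, (2) subjects who switched from 70mg to 140mg at any time during the study", then "subjects who switched from 140mg to 70mg at any time during the study", then always 140 mg, then all subjects combined. The same groups serve all treatment-emergent events, serious events, events leading to withdrawal of drug, device effects, treatment-related events, fatal events and the events of interest.

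The counting window is a single one. SAP 5.1.3 takes events from first dose "and up to the End of Study date", and SAP 5.4.3 says "The efficacy and safety analyses will be summarized for the OLTP". SAP 5.6 divides subjects with at least one event by subjects entering the period: "For subjects with multiple occurrences of the same event, the event will only be counted once per subject".

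On switching, Protocol 1.1 and 4.2 allow one adjustment, at the week 12 visit. SAP 5.5 adds that "subjects could switch dose before or after week 12 if needed (e.g., adverse event" is an example of why, and defines a switch as any change from the baseline dose during the study.

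Exposure is treated differently. SAP 5.6 splits duration at the first switch ("Duration on or after the First Switch = Minimum (Last Dose Date + 27, EOS Date" begins the second part), and SAP 9.6.2 summarizes total length of exposure "and exposure by dose level". No adverse event count or rate is matched to that split. The grade tables in SAP 9.6.1 and the tables in Protocol 9.3.2.3.1 name no dose split. Grouping by day-1 dose is specified for efficacy (SAP 9.1) and disposition (SAP 9.2), not for adverse events.

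**The concern.** The five groups are the only planned adverse event incidence display that separates the doses. Two features limit what it can tell a reader.

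First, the 70-to-140 and 140-to-70 columns pool events before and after the change. A reader cannot see which dose a subject was on when an event started.

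Second, all four dose columns are defined by what happens after baseline. An event that prompts a switch takes the subject out of an always column and is then counted in a switch column. A subject who leaves before any switch stays in an always column with shorter follow-up. Incidence is not adjusted for time at risk.

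There is also a small gap in assignment. A subject who goes 70, 140, 70 meets the definitions of both switch groups, and SAP 9.6.1 has no rule for this. SAP 5.6 credits all time from the first switch onward to one block, so a second change would not be separated either.

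At stake is the interpretation of the safety tables, including the events of interest. The primary endpoint is not affected.

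**Working it through.** The plan gives no adverse event or switch rates, so it contains no figure to reproduce. Only step 1 rests on the documents alone. Steps 2 and 3 are illustrations.

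**1. Share of a switch column's exposure that is on the starting dose.** Inputs: dosing every 4 weeks, so doses on days 1, 29, 57, 85, 113 and 141; end-of-study target day 169 (SAP Table 4); duration formulas from SAP 5.6.

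- Before a week-12 switch: min(57 + 27, 85 − 1) − 1 + 1 = 84 days.
- On or after it: min(141 + 27, 169) − 85 + 1 = 84 days.
- Share on the starting dose: 84/168 = 50%.
- With the week-12 visit at ±7 days: 77/168 = 45.8% to 91/168 = 54.2%.
- For a switch at week 4, 8, 16 or 20 the share is 17%, 33%, 67% or 83%.

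**2. What that does to a switch column.** Assumptions, none from the documents: equal event hazard at both doses, switch at week 12 unrelated to events, follow-up to week 24, mean of m events per subject, and between-subject variation as gamma frailty with variance 1.

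- P(any event) = 1 − 1/(1 + m). P(event in one 12-week half) = 1 − 1/(1 + m/2).
- At m = 0.5 the column shows 1 − 1/1.5 = 33.3%, while 1 − 1/1.25 = 20.0% had an event after the switch.
- Affected subjects with a pre-switch event: 20.0/33.3 = 60%. With pre-switch events only: (33.3 − 20.0)/33.3 = 40%.
- For m = 0.2 and 1.0 these shares are 55% and 67% (pre-switch event), and 45% and 33% (pre-switch only).
- Without frailty, P = 1 − exp(−m) and 1 − exp(−m/2). At m = 0.5 this gives 39.3% and 22.1%, a pre-switch share of 56%. The frailty assumption changes the figures, not the message.

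**3. What switching that depends on events could do.** Simulation with 2,000,000 subjects per scenario, equal hazard at both doses, m = 0.5, the same frailty, 5% dropout spread over weeks 0 to 12, switch at week 12. Switch probabilities are assumed and given as with / without an earlier event. Table entries are incidence in %.

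| Scenario | Always 70 | 70 to 140 | 140 to 70 | Always 140 | Always 70 minus 70-to-140 | Rate ratio 70 vs 140 by dose at onset |
|---|---|---|---|---|---|---|
| Up 15/35%, down 15/2% | 35.3 | 24.8 | 71.3 | 30.4 | +10.5 | 1.05 |
| Up 25/35%, down 5/1% | 33.5 | 29.3 | 63.1 | 31.7 | +4.2 | 1.02 |
| Up 30/30%, none down | 31.8 | 33.4 | – | 32.2 | −1.6 | 1.01 |
| Up 35/25%, none down | 30.1 | 38.2 | – | 32.2 | −8.1 | 0.98 |

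The true ratio is 1 throughout. A repeat run agreed within simulation error. Over m = 0.2 to 1.0, the gap is about +2 to +14 points if events deter a move to 140 mg, about −5 to −10 if they encourage it, and −0.9 to −2.3 if they are unrelated to it. That last gap arises because early dropouts stay in the always column.

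In the first scenario, pooling the first two columns and the last two gives 32.2% each. With one change per subject, incidence by day-1 dose is therefore recoverable.

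**4. Whether an onset table could use the SAP 5.6 exposure as it stands.** Exposure stops at last dose + 27 days, but events count to end of study.

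- After a week-20 dose, exposure ends on day 141 + 27 = 168, one day before day 169.
- After a last dose at week 8 (day 57), it ends on day 84. With follow-up to day 169, that leaves 85 days outside it.
- Assume 5% to 20% stop drug early, with last doses evenly spread from day 1 to week 16 (mean exposure 84 days), and 50% to 100% of them stay to day 169.
- Low end: exposure 0.95 × 168 + 0.05 × 84 = 163.8 days; follow-up 0.95 × 169 + 0.05 × (0.5 × 169 + 0.5 × 84) = 166.9; overstatement 166.9/163.8 − 1 = 1.9%.
- High end: exposure 0.8 × 168 + 0.2 × 84 = 151.2; follow-up 169; overstatement 169/151.2 − 1 = 11.8%.

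Numerator and denominator therefore need the same window.

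**The case against.** The strongest reply is that nothing planned is wrong. SAP 2.2 and Protocol 3.2 plan no formal testing, and no objective compares doses or concerns safety. Protocol 9.3.2.3.1 asks only for incidence by system organ class and preferred term, so the SAP columns already go further. The labels are accurate, and the SAP never calls the columns a dose comparison. All of this stands, and it caps the weight of the point.

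Events on treatment in the two always columns did occur on one dose. That also stands: unclear attribution is confined to the switch columns. Selection still applies to all four.

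The numbers in steps 2 and 3 come from assumed rates. That is correct. A reader might infer that the display will make one dose look safer. The documents do not support this: they give no switch or event rates, and SAP 5.5 names an adverse event as a reason without saying in which direction. SAP Table 8 drops the dose-switch covariate for the 140 mg group, which may mean few or no moves from 140 to 70 mg.

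A reader might also infer that the SAP permits repeated switching. It says only that a switch could fall before or after week 12. Two changes would depart from the protocol's single adjustment, so the missing assignment rule concerns a rare case.

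The reason for a dose change (Protocol 6.4.2.1) and the action taken for each event (Protocol 11.4.4) are recorded, so event-prompted switches can be traced. No table of them is planned.

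Finally, a dose-at-onset table has its own difficulty with incomplete start dates. SAP Table 5 sets a missing day to the 1st of the month, which would tend to place an event in the switch month before the switch, and it leaves a fully missing date unimputed. This objection is right, and the fix has to deal with it.

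**Conclusion.** The point holds as a worthwhile, low-cost improvement to a descriptive safety display. In the switch columns, events on the starting dose are mixed with later events; for a compliant week-12 switcher half of the exposure is on the starting dose. Because membership of the four dose columns is post-baseline and can depend on an event, they should not be read as incidence by dose. The overall column is sound.

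The 50% follows from the dosing schedule and SAP 5.6. Every other percentage rests on assumed event rates, frailty, switch probabilities or stopping rates. The illustrations show that sizeable gaps of either sign can arise with no dose effect, while rates by dose at onset stay near equality (0.98 to 1.05 at a mean of 0.5 events). They do not show that this will happen in this trial.

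**What to change.** In SAP 9.6.1:

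- Add one table for all treatment-emergent events, serious events and events of interest, by most recent dose at event onset, with exposure-adjusted rates.
- Count events and person-time over the same window. Either use the SAP 5.6 exposure windows and list later events separately, or extend the last dose's person-time to end of study.
- Derive person-time across all dose changes, not only the first.
- State how incomplete start dates are assigned. The before/after flag in SAP Table 5 refers to the first dose, so it does not settle which side of a switch an event falls on. Where other recorded information does, such as the action taken, use it. Show the remaining events in the switch month, and those with no date, as dose at onset unknown.
- State which switch column a subject with more than one change enters, and reconcile SAP 5.5 with the protocol's single week-12 adjustment.
- Footnote that the switch columns include pre-switch events. Add that dose is investigator-chosen and, per SAP 4.1, highly correlated with country, so no display is an unconfounded dose contrast.
- Optionally, show subtotals by day-1 dose.

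The cost is a derived dose-at-onset variable, a window rule, person-time by dose and a few table shells, all from data already collected. A subject can appear under both doses, and some selection from non-random switching remains.
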